Multiple doses of 10 mg/kg IV were safe and tolerated in Study AACC. Although infusion reactions were observed in 6 out of 51 patients dosed with LY3002813, there were no infusion reactions in the 10 mg/kg dose cohort, despite the presence of ADAs. Clinical dosing of single dose of 20 mg/kg or multiple dosing of 10 mg/kg in Study AACD will only be initiated after safety review of the single 10-mg/kg dose of LY3002813.

MRI safety monitoring will occur 4 weeks after the first dose, every 12 weeks from the first dose, and up to 12 weeks after the last dose, with acquisition of sequences appropriate for

detecting vasogenic edema and microhemorrhage. These MRIs and MRIs at additional time points (ie, at 24 weeks, 48 weeks, and 72 weeks) will also provide volumetric and other imaging biomarker assessments. Microhemorrhages are believed to indicate a higher risk for macrohemorrhage as well as for the presence of significant amyloid angiopathy, and there appears to be a risk of microhemorrhage with antiamyloid treatment in preclinical models and in humans (eg, bapineuzumab, gantenerumab, aducanumab [Black et al. 2010]) as well. Although there was no evidence of ARIA-E by MRI at up to 10 mg/kg LY3002813 in Study AACC, this study will continue to monitor ARIA-E (and ARIA-H). The screening MRI scan will be used to exclude patients with >4 microhemorrhages. The 12-week interval between MRI scans is considered appropriate given the lack of ARIA-E observed up to 10 mg/kg LY3002813 in Study AACC.

8. Study Population

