10.6. Safety Evaluations

Investigators are responsible for monitoring the safety of patients who have entered this study and for alerting Lilly or its designee to any event that seems unusual, even if this event may be considered an unanticipated benefit to the patient.

The investigator is responsible for the appropriate medical care of patients during the study. Planned safety assessments and measures are detailed in Section 10.6.3, but additional assessments and safety tests may be performed at the investigator's discretion.

The investigator remains responsible for following, through an appropriate health care option, AEs that are serious, considered related to study treatment or the study, or that caused the patient to discontinue before completing the study. The patient should be followed until the event is resolved or explained. Frequency of follow-up evaluation is left to the discretion of the investigator.

In addition to records of observations made at specific times, unexpected signs and symptoms and concomitant medications will be recorded in the clinical trial records throughout the study.

Safety monitoring will include MRIs, AEs, ECGs, vital signs (blood pressure, pulse rate, and temperature), physical and neurological examinations, C-SSRS, and safety laboratory tests (including LP clinical laboratory tests).

For Part A, MRI safety monitoring will consist of a baseline MRI, a Week 4 postdosing MRI, and a Week 12 postdosing MRI, with sequences appropriate for detecting vasogenic edema and microhemorrhage. MRIs at baseline, 24 weeks, 48 weeks, and 72 weeks are for volumetric assessment. Additional MRI measures may be obtained at these ARIA-related and/or MRI time points.

For Parts B and C, MRI safety monitoring will consist of a baseline MRI, a Week 4 postdosing MRI, and a Week 12 postdosing MRI, as well as MRIs every 12 weeks until 48 weeks (Part B) and 12 weeks (Part C) after the last dose. MRIs at baseline, 24 weeks, 48 weeks, and 72 weeks are for volumetric assessment. Additional MRI measures may be obtained at these ARIA-related and/or MRI time points.

Determination of the number of microhemorrhages will be required to be assessed on a 1.5T or 3T MRI, as the greatest understanding of the number of microhemorrhages and their relationship to disease are associated with these magnet strengths.

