18F-AV-1451 PET scans will be obtained from each randomized patient at pre-dose Visit 4 and at Visit 17 approximately 72 weeks post-dose. The change in SUVr as the response variable and the IV dose group as the explanatory factor with the baseline SUVr as a covariate. The primary contrast will be the mean change in SUVr of each IV dose group relative to placebo. A summary table of the LSmean results and contrast p-value will be generated. In addition, a graphical display of the LSmean and confidence interval on the y-axis and the IV dose-groups and placebo along the x-axis.

Magnetic resonance imaging changes in volume over the course of the study will be explored, and exploratory evaluation of whole brain and anatomically localized structural changes will be summarized (including, but not limited to, whole brain, ventricle, and hippocampus). Magnetic resonance imaging volumetric assessments will be obtained at baseline, 24 weeks, 48 weeks, and 72 weeks as applicable. An MMRM will be constructed by fitting treatment and study visit as fixed effects. Response variables are brain structural changes of whole brain, ventricle, and hippocampal volumes.

Additionally, the relationship between LY3002813 serum exposure and imaging endpoints may be explored graphically or by additional exploratory analyzes.

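### The MRI-volume model has no baseline-volume term and no stated scale of change, which may leave avoidable noise in the dose contrasts, mainly for ventricles

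*SAP*

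**What the plan says.** SAP section 4.2.5.1 gives the whole MRI-volume model in one sentence: "An MMRM will be constructed by fitting treatment and study visit as fixed effects". The outcomes follow: "Response variables are brain structural changes of whole brain, ventricle, and hippocampal volumes". No baseline volume, head-size term or scale of change is named. Protocol section 11.2.5.1 describes the same two-term model and makes it optional.

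The neighbouring analyses are fuller:

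- **Tau PET (SAP 4.2.5.1):** "The change in SUVr as the response variable and the IV dose group as the explanatory factor with the baseline SUVr as a covariate".
- **CSF (SAP 4.2.5.3):** the ANCOVA also fixes baseline concentration as a covariate.
- **Florbetapir SUVr and cognition (SAP 4.2.5.1 and 4.2.5.2):** these MMRMs allow a baseline covariate, name percent change as a second response, and include a treatment-by-visit interaction.

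On timing, the SAP states: "Magnetic resonance imaging volumetric assessments will be obtained at baseline, 24 weeks, 48 weeks, and 72 weeks as applicable". Protocol 10.6 agrees ("MRIs at baseline, 24 weeks, 48 weeks, and 72 weeks are for volumetric assessment"), and so does Protocol 10.5.2. Protocol 10.6 leaves other time points optional: "Additional MRI measures may be obtained at these ARIA-related and/or MRI time points". Protocol 7.2 has just described safety MRIs at 4 weeks, every 12 weeks, and up to 12 weeks after the last dose. It then goes further: "These MRIs and MRIs at additional time points (ie, at 24 weeks, 48 weeks, and 72 weeks) will also provide volumetric" assessments.

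**The concern.** Loss or enlargement of a structure may be roughly proportional to its size. If so, the same percentage change gives more millilitres in a patient with larger ventricles. The active arms hold 6 or 9 patients and each cohort has 2 or 3 on placebo, so mean baseline size will differ between groups by chance. An absolute-change analysis without a size term carries that difference into the dose contrast.

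Change in MRI measures is a stated exploratory objective, and the baseline MRI is already taken at screening Visit 2. The noise is therefore avoidable with data in hand. The timing conflict is a separate matter: a programmer cannot tell from the documents whether volumes from the remaining safety MRIs (for example Weeks 12 and 36 in Parts B and C) belong in the analysis.

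**Working it through.** **Inputs from the documents.** Cohorts 1-3 have 6 active and 2 placebo patients, and Cohorts 4-7 have 9 and 3. The total is 3 x 8 + 4 x 12 = 72, which reproduces the planned completers. Pooling placebo within a Part gives 6 per Part, but SAP 4.2.3 states this only for the baseline table. Neither document gives an SD or CV for any volume, or a sample size for this analysis.

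**Assumptions.** Change = size x rate, with size and rate independent. The size CV is *c* and the CV of individual rates of change is *s*. There is one change value per patient.

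**Step 1: chance imbalance in size.** SE of the relative size difference = *c* x sqrt(1/n1 + 1/n2).

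- 9 v 6: factor sqrt(1/9 + 1/6) = 0.527, giving 5.3% at *c* = 10% and 26% at *c* = 50%.
- 6 v 6: factor sqrt(1/6 + 1/6) = 0.577, giving 5.8% and 29%.

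This is the typical spurious shift in an absolute-change contrast, as a fraction of the mean change.

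**Step 2: what a baseline covariate removes.** Relative to the squared mean change, the per-patient variance of absolute change is c² + s² + c²s². A linear baseline term explains c² and leaves s² + c²s². Before the cost of estimating the covariate, the cut in contrast SD is 1 - sqrt[(s² + c²s²)/(c² + s² + c²s²)].

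| c | s | ratio of variances | cut in SD |
|---|---|---|---|
| 10% | 50% | 0.2525/0.2625 | 1.9% |
| 30% | 50% | 0.2725/0.3625 | 13.3% |
| 50% | 50% | 0.3125/0.5625 | 25.5% |
| 30% | 100% | 1.09/1.18 | 3.9% |
| 50% | 100% | 1.25/1.50 | 8.7% |

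**Step 3: simulation, which includes the lost degree of freedom.** SD of the dose-placebo contrast, in units of mean change, 4,000 trials per case:

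| Comparison | c | s | absolute | with baseline | percent change |
|---|---|---|---|---|---|
| 6 v 18, all groups in one model | 10% | 50% | 0.239 | 0.238 | 0.235 |
| 6 v 18, all groups in one model | 30% | 50% | 0.284 | 0.246 | 0.236 |
| 6 v 18, all groups in one model | 50% | 50% | 0.348 | 0.261 | 0.233 |
| 6 v 18, all groups in one model | 50% | 100% | 0.576 | 0.523 | 0.473 |
| 9 v 6 | 50% | 50% | 0.392 | 0.290 | 0.263 |

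The 18 assumes placebo pooled across all cohorts, which the SAP does not state for this model. The 9 v 6 row needs pooling only within a Part. I repeated the runs for 6 v 6 and 9 v 6 alone, a 9, 9, 6 Part and all groups together, with normal and lognormal sizes. At *s* = 50% and *c* = 30-50% the covariate cut the SD by 8-27%. At *s* = 100% the cut was 0-4% for *c* = 30% and 5-11% for *c* = 50%.

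**Step 4: cost where size hardly varies.** With two small groups fitted alone and *c* = 10%, the covariate raised the SD from 0.297 to 0.309 (6 v 6, *s* = 50%), which is 4%. At *s* = 100% it rose from 0.580 to 0.612, about 5.5%.

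**Step 5: validity.** With 20,000 trials per case at *c* = 10%, type I error was 4.6-5.4% with or without adjustment, and mean bias was near 0. In the runs at *c* = 30-50% it was 4.1-5.7%.

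**The case against.** Four objections carry weight.

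- **The scale is unstated.** A reader might infer that the plan chooses raw millilitres. The SAP does not say so; percent change would fit its wording and would remove most of the issue. This stands: the documented gap is silence about scale, and the noise arises only if absolute change is used.
- **Randomisation already covers it.** A reader might infer that size imbalance biases the contrasts or produces false positives. It does not. Additive size differences cancel in a within-patient change, and the proportional part is chance variation that the standard error includes. This stands too: only precision is at issue.
- **The CVs are assumed.** This stands. At 10% there is nothing to gain, and a covariate can cost a little in the smallest comparisons.
- **The plan is flexible.** These analyses are declared exploratory and can change without a protocol amendment, and Protocol 11.2.3 lets characteristics such as sex and height enter PD analyses. That lowers the stakes, but a term fixed in advance is still better than one chosen after seeing the volumes.

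It can also be said that the missing treatment-by-visit interaction is a larger gap in this model. It is a real omission beside the SUVr and cognition models, and can be settled in the same edit.

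On visits, a reader might infer that the SAP wrongly discards safety scans, that doing so causes the size imbalance, or that adding them would sharpen a slope. The SAP list matches Protocol 10.5.2 and 10.6. In Parts B and C, Weeks 24, 48 and 72 fall within the 12-weekly safety series. Leaving out scans cannot create imbalance in baseline size. The planned model fits visit as a fixed effect and estimates no slope.

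**Conclusion.** The point holds as a low-cost improvement to an exploratory analysis. The MRI-volume model omits a baseline term that the sister models fix or allow, and it leaves the scale of change open. If absolute change is used, the result is avoidable noise. It is negligible at a size CV near 10%. At an assumed size CV of 30-50% and a rate CV of 50%, roughly 8-27% of the contrast SD could be removed, falling to about 0-11% at a rate CV of 100%. These figures rest on change being proportional to size and on CVs that the documents do not supply. The documents do not support a claim of bias or inflated type I error. The conflict over which MRIs provide volumes is real but separate: Protocol 7.2 stands against Protocol 10.5.2, 10.6 and the SAP.

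**What to change.** In SAP 4.2.5.1, and for consistency in Protocol 11.2.5.1, state the scale of change. Then either add the Visit 2 baseline volume of the same structure as a fixed covariate in each MRI-volume model, or analyse log volume or percent change. State in the same place whether placebo is pooled and whether treatment-by-visit is included.

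Separately, reconcile Protocol 7.2 with Protocol 10.5.2, 10.6 and the SAP on which MRI visits supply volumes. If more visits are added, the interaction matters more. With equal weights, a treatment main effect over Weeks 24, 48 and 72 is centred at Week 48. Adding Weeks 12, 36 and 60 moves the centre to Week 42, which dilutes a linearly growing effect by 6/48 = 12.5%.

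The cost is SAP wording and, for the covariate, one degree of freedom, with a slight loss of precision where size hardly varies. The baseline scan is already collected. Extra image processing arises only if volumes from further visits are wanted.

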#### **4.2.5.2. Assessment of Cognitive and Functional Measurements**

Statistical assessment of the total cognitive measurement change from baseline will be analyzed by an MMRM. The response measurements are (1) change from baseline and (2) the percent change from baseline for ADAS-Cog (14), ADL, MMSE, FCSRT-IR total, CDR-Sum of Boxes, and NTB. Baseline for each measurement is defined as the pre-dose measurement obtained at screening Visit 3 or prior to randomization. The change from baseline and percent change are computed from the total cognitive measurement obtained from the scheduled study visits at weeks 24, 48, and 72. Patients have the option to have the cognitive measures assessed taken at early discontinuation. For early discontinuations, cognitive value will be mapped to the nearest scheduled study visit at week 24, 48, or 72. The planned analyses is an MMRM using an appropriate covariance structure with fixed effects of treatment doses (LY3002813 and placebo), study visit, and interaction between treatment and visit. A baseline covariate adjustment may be used. The primary comparison is between LY3002813 IV doses and placebo for change from baseline or percent. A table of the LSmeans per dose group with associated p-value contrast to placebo will be constructed. A graphical summary of the LSmeans and a mean confidence interval on the y-axis and the study visit on the x-axis for each IV dose-group. Given the small sample size of n=6 patients per IV dose group, simplification of the mixed-effects model might be considered.

In addition to the MMRM analysis, a Bayesian posterior probability may be computed for each LY3002813 dose compared to placebo. For each dose, the credible interval will be computed for each dose relative to placebo. This analysis may be omitted if access to appropriate software such as SAS version 9.4 is not available.

#### **4.2.5.3. Pharmacodynamic Cerebrospinal Fluid Estimation**

The CSF results from the LPs taken pre- and postdose will be analyzed to estimate the mean change and percent change from predose. The dependent variables are A $\beta$ 1-40, A $\beta$ 1-42, , total tau, and phospho-tau concentrations. Using an ANCOVA model, IV dosing regimen will be a fixed effect with the baseline concentration as a covariate in the model. These analyses are considered exploratory in order to estimate mean change and the variance of the change following IV single, multiple and chronic doses of LY3002813. A logarithmic transformation may be used to ensure valid statistical estimation properties.

In addition to these analyses, correlation analyses between changes in CSF biomarkers (A $\beta$ 1-40, A $\beta$ 1-42, total tau, phospho-tau), or imaging endpoints (MRI measures, or SUVr from florbetapir scans) with posthoc serum AUC estimates derived from the PK model (or an alternative measure of exposure if deemed appropriate) may be completed. For SUVr, this will be conducted for the individual regions (if collected) and the total SUVr. Additionally, CSF and/or serum LY3002813 exposures may be related to CSF biomarkers, as appropriate.

#### **4.2.5.4. Plasma A $\beta$**

Plasma A $\beta$  will be analyzed to estimate the mean change from predose. The dependent variables will be A $\beta$ 1-40 and A $\beta$ 1-42.

Dosing regimen will be a fixed effect in the model and time may be included as a repeated effect. These analyses are considered exploratory in order to estimate if there is mean change following doses of LY3002813. If required, a logarithmic transformation may be considered.

### **4.2.6. Pharmacokinetic/Pharmacodynamic Analyses**

Exploratory correlational analyzes may be conducted to describe the relationship between exposure and changes in the florbetapir SUVr; MRI of whole brain, ventricle, and hippocampus volumes; CSF concentrations of abeta, tau and ptau; maximum ADA levels; and number AEs related to infusion reactions. It is intended that these analyses will be descriptive graphs in nature as a function of LY3002813 dose, exposure, and/or time from study entry; however, the relationship may also be described using a modeling approach, if appropriate.

### **4.2.7. Safety Analyses**

#### **4.2.7.1. Clinical Evaluation of Safety**

All investigational product and protocol procedure AEs will be listed. At a minimum, all safety data will be summarized using descriptive methodology.

The incidence of symptoms for each IV dose will be presented by severity and by association with investigational product, as perceived by the investigator. Symptoms reported to occur before randomization will be distinguished from those reported as new or increased in severity during the study. Each symptom will be classified by the most suitable term from the medical regulatory dictionary.

The number of investigational product-related SAEs will be reported.

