7.1. Summary of Study Design

[figure not shown]
This is a Phase 1b, patient- and investigator-blind, randomized within cohort, placebo-controlled, parallel-group, single- and multiple-dose study in patients with MCI due to AD or mild to moderate AD to assess the safety, tolerability, PK, and PD of single and multiple IV doses of LY3002813.

This study (Study AACD) will enroll patients with MCI due to AD, mild AD, or moderate AD with amyloid deposition confirmed by florbetapir PET imaging using National Institute on Aging-Alzheimer's Association (NIAAA) work group consensus guidelines (Albert et al. 2011; McKhann et al. 2011). This study will be conducted at sites in multiple countries, including the United States and Japan. Up to 150 patients may be enrolled so that approximately 72 patients (7 dosing cohorts of 8 to 12 patients) complete the study.

[figure not shown]
The study will be conducted in at least 7 cohorts ([Figure AACD.7.1](#)):

- Cohort 1: 10 mg/kg IV single dose
- Cohort 2: 20 mg/kg IV single dose
- Cohort 3: 40 mg/kg IV single dose
- Cohort 4: 10 mg/kg IV every 2 weeks (Q2W) for 24 weeks
- Cohort 5: 20 mg/kg IV Q2W for 24 weeks
- Cohort 6: 10 mg/kg IV Q4W for up to 72 weeks
- Cohort 7: 20 mg/kg IV Q4W for up to 72 weeks

[figure not shown]
Part A: Single dose; 72-week follow-up (Cohorts 1 & 2), 24-week follow-up (Cohort 3)

Part B: 24-weeks, Q2W multiple dose treatment; 48-week follow-up

Part C: Chronic dose, 72-week, Q4W multiple dose treatment; 12-week follow-up

Abbreviations: f/u = follow up; IV = intravenous; MRI = magnetic resonance imaging; PET = positron emission tomography; Q2W = every 2 weeks; Q4W = every 4 weeks; x = times.

Assessments: A = amyloid PET; I = immunogenicity; M = MRI; T = tau PET; C = cognition; F = cerebrospinal fluid.

D = dosing; S = 4 week safety review of Cohort 2.

Follow-up assessments (immunogenicity, I; MRI, M) 12 weeks after last dose for Cohorts 6 and 7.

Note: vertical lines indicate 4-week intervals. Additional immunogenicity assessments will be performed every 12 weeks up to 48 weeks after the last dose of LY3002813 if the antibody titer has not returned to baseline.

Figure AACD.7.1. Study design.

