7.1.3. Part A: Single Dose Cohorts (Cohorts 1 through 3)

Safety, PK, and PD will be assessed in Cohorts 1 through 3 after single doses of LY3002813 or placebo. The planned doses are 10, 20, and 40 mg/kg IV for Cohorts 1, 2, and 3, respectively; with 8 patients (6 LY3002813; 2 placebo) planned to be enrolled in each cohort. Dose escalation will only occur after the safety from the preceding cohort has been established in at least 4 patients receiving LY3002813 and 1 receiving placebo. Safety data will be collected at least 1 week after dosing for dose escalation to Cohort 2 and at least 4 weeks after dosing for dose escalation to Cohort 3. Enrollment in Cohorts 2 and 3 will only commence once enrollment into the preceding cohort has completed. Safety, PK, and PD will be assessed at regular intervals for approximately 72 weeks (in Cohorts 1 and 2) or 24 weeks (in Cohort 3) after starting the dosing with study drug ([Attachment 1](#)).

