#### **4.2.3. Study Participant Characteristics**

The patient's age, sex, race (Non-Japanese and Japanese), weight, height, smoking habits, APOE4 status, MMSE baseline value, FCSRT-IV total score, CDR-Sum of Boxes score, ADAS-Cog (14), NTB total score, and ADL24, number of ARIA-E, ARIA-M and/or other demographic characteristics will be summarize in baseline table for all IV dose group and subset by Part A Single IV doses, Part B Multiple doses (Q2W dosing), and Part C Chronic doses (Q4W dosing). The placebo-groups will be combined within the 3 study Parts (A,B, and C). In addition, a baseline table will be constructed for all Japanese patients and a similar baseline summary table will constructed for all non-Japanese patients. A complete patient listing of the baseline characteristics will be constructed for each IV dose group.

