#### 4.2.7.2. Statistical Evaluation of Safety

Safety parameters that will be assessed include safety clinical laboratory parameters, vital signs, and ECG parameters. The parameters will be listed and summarized using standard descriptive statistics. Additional analysis will be performed if warranted upon review of the data.

A shift table for each IV dose will be constructed to assess the MRI measurement pre- and postdose for changes and additions of vasogenic edema and microhemorrhages (ARIA-E and ARIA-H)

Suicide-related thoughts and behaviors based on the C-SSRS will be listed by patient. Only time points and patients that show ideation/behavior of suicide will be displayed (ie, all “no” responses may not be displayed).

Exploratory analyses of Fridericia's corrected QT interval (QTcF) data from ECG monitoring in a Phase 1 trial are performed to judge the extent and/or risk of QT prolongation. There will be an exploratory assessment of potential prolongation by examining mean change in QTcF as a function of serum drug concentration obtained and an inspection of the upper confidence limit relative to a value of 10 msec, which is consistent with International Conference on Harmonisation (ICH) guidance. Frequency tables of QTc changes from baseline and large QTc values may also be obtained in accordance with ICH guidance.

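### AEs and ARIA are tabulated as crude incidence by dose over scheduled follow-up of 24, 72 or 84 weeks, so regimen is confounded with observation time

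*SAP*

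**What the plan says.** SAP 4.2.7.1 describes the adverse-event summary in these words: "The incidence of symptoms for each IV dose will be presented by severity and by association". For ARIA, SAP 4.2.7.2 states: "A shift table for each IV dose will be constructed to assess the MRI measurement pre- and postdose". It does not say which postdose scans count. The registry tables in SAP 4.4 use participants at risk as the denominator, by treatment group. All of this is descriptive, and no section gives a common window, a person-time rate or a time-to-event summary for AEs or ARIA.

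Follow-up differs by design. Protocol 7.1.3 assesses Part A "for approximately 72 weeks (in Cohorts 1 and 2) or 24 weeks (in Cohort 3" respectively. The other parts are given in Protocol 7.1: "Part B: 24-weeks, Q2W multiple dose treatment; 48-week follow-up" and "Part C: Chronic dose, 72-week, Q4W multiple dose treatment; 12-week follow-up".

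The SAP was approved in December 2015. The protocol amendment that cut Cohort 3 to 24 weeks was approved in December 2017, so the SAP has no rule for the resulting gap.

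On placebo, SAP 4.2.3 says: "The placebo-groups will be combined within the 3 study Parts (A,B, and C". That sentence governs baseline tables. SAP 4.3 summarises interim safety data by IV dose group and placebo without saying how placebo is grouped.

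**The concern.** A patient watched for 72 weeks has three times as long to report an event as one watched for 24. If incidence is a simple proportion per dose, the highest single dose has the shortest exposure to counting, and its proportion falls for that reason alone. The 84-week Part C cohorts are pushed the other way.

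Safety is a secondary objective. Protocol 5.2 names a low incidence of ARIA-E and ARIA-H among the conditions for further development and dosing selection. Readers will compare the dose columns whether or not a test is attached, so a dose trend produced by follow-up length could be taken for a drug effect, or could hide one.

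**Working it through.** **Plan figures.** The documents give no safety rate or power to reproduce. The cohort sizes do reproduce: 3 × (6 + 2) + 4 × (9 + 3) = 72 planned completers, of whom 3 × 2 + 4 × 3 = 18 are on placebo. The visit days in Attachment 1 give (169 − 1)/7 = 24, (505 − 1)/7 = 72 and (589 − 1)/7 = 84 weeks.

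**Model (an assumption, not in the documents).** Every arm has the same constant hazard, so the drug has no effect, and nobody drops out. With h the risk over 24 weeks, the risk by week w is F(w) = 1 − (1 − h)^(w/24).

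**ADA extension.** Protocol 10.4.1 continues AE collection every 12 weeks, up to 48 weeks after the last dose, for patients with a positive titer that has not returned to baseline. Cohort 3 could therefore reach Week 48. Cohorts 1-2 are already past that limit and Part B is at it (24 + 48 = 72).

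| Quantity | h = 10% | h = 20% | h = 30% |
|---|---|---|---|
| (a) Cohort 3, 24 weeks: h | 0.100 | 0.200 | 0.300 |
| (b) Cohorts 1-2 and Part B, 72 weeks: 1 − (1 − h)^3 | 0.271 | 0.488 | 0.657 |
| (c) Part C, 84 weeks: 1 − (1 − h)^3.5 | 0.308 | 0.542 | 0.713 |
| (d) Cohort 3 active extended to 48 weeks: 1 − (1 − h)^2 | 0.190 | 0.360 | 0.510 |
| (e) Part A placebo if pooled: (2a + 4b)/6 | 0.214 | 0.392 | 0.538 |
| 40 mg/kg vs 10 and 20 mg/kg single dose, scheduled: a/b | 0.37 | 0.41 | 0.46 |
| Same, with extension: d/b | 0.70 | 0.74 | 0.78 |
| 40 mg/kg vs pooled Part A placebo, scheduled: a/e | 0.47 | 0.51 | 0.56 |
| Same, active patients extended, placebo not: d/e | 0.89 | 0.92 | 0.95 |
| 40 mg/kg vs Cohort 3's own placebo, scheduled: a/a | 1.00 | 1.00 | 1.00 |

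Over a wider grid (72-week risk from 10% to 90%), the ratio to pooled Part A placebo is 0.44 to 0.69 on scheduled follow-up and 0.87 to 1.01 with full extension. With extension, the direction reverses once the 24-week risk exceeds 50%. If only the active patients of Cohort 3 were extended, even the comparison with their own placebo would become unequal, in the opposite direction: 0.360/0.200 = 1.80 at h = 20%.

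**ARIA.** Protocol 10.6 sets the Part A safety MRIs at Weeks 4 and 12 in all three cohorts and calls the Week 24, 48 and 72 scans volumetric. Within Part A, imbalance arises only if the Week 48 and 72 scans of Cohorts 1-2 enter the shift table. Against Parts B and C the difference is explicit: safety MRIs run every 12 weeks until 48 weeks (Part B) or 12 weeks (Part C) after the last dose, that is to Week 72 or Week 84. MRI is not among the ADA-extension assessments.

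**Infusion reactions.** Protocol 5.1 reports that in the earlier study they began during the infusion or within 30 minutes of its end. After a single dose, longer follow-up adds nothing to their count.

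**With a common 24-week window.** Every group has risk h, so the ratio is 1.00 at every h. At a 72-week risk of 50% (20.6% by Week 24), the chance that 40 mg/kg (n = 6) shows a lower proportion than pooled Part A placebo (n = 6) falls from 68% to 36%. It then equals the chance that it shows a higher one.

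**The case against.** The strongest reply is that nothing here is a planned comparison. The safety tables are descriptive, no contrast or risk ratio is specified, and the Protocol 5.2 criteria are absolute rather than rankings. The hazard is assumed, and events clustered soon after dosing would shrink the effect. The interim safety reviews in Protocol 11.3 already take data to Day 169 for Cohorts 3, 4 and 5. All of this stands, and it limits the severity. It does not remove the problem: the columns will be read side by side, and the final tables carry no Week 24 cut.

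A reader might infer that the plan will make 40 mg/kg look safer than placebo. The documents do not support that. Pooling of placebo within Part is stated only for baseline tables. Against Cohort 3's own placebo there is no bias on scheduled follow-up, although two patients give little information. For AEs, the ADA visits can close most of the gap with pooled Part A placebo. More than 90% of treated patients with AD in the earlier study developed ADAs, so these visits are likely to be used. They also make follow-up depend on a response to treatment, which is a further reason for a fixed window.

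A reader might also infer a general ARIA or infusion-reaction bias. Within Part A, the safety MRIs are the same in all three cohorts and infusion reactions do not depend on follow-up length.

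**Conclusion.** The point holds for side-by-side comparison of dose groups. The planned AE summary confounds regimen with observation time, and so does the ARIA summary when Cohort 3 is set against Parts B and C. For AEs, a drug with no effect would show 40 mg/kg at about 0.41 times the incidence of the lower single doses at h = 20% (0.37 to 0.46 for h from 10% to 30%), or about 0.74 with full ADA extension. These sizes rest on a constant, equal hazard and no dropout.

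Distortion against placebo is conditional on an unstated pooling choice: about 0.5 on scheduled follow-up and roughly 0.9 to 1.0 with full extension. ARIA distortion within Part A is conditional on which scans are counted. This is a correction the SAP should make, not a demonstrated bias in favour of 40 mg/kg.

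**What to change.** In SAP 4.2.7.1 and 4.2.7.2:

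- Present between-regimen and placebo incidence of AEs, ARIA-E and ARIA-H over first infusion to Week 24, a period scheduled in all seven cohorts.
- For ARIA in that window, use the Week 4, 12 and 24 MRIs common to all cohorts. Confirm that the Week 24 scan, labelled volumetric in Part A, is read for ARIA there. If it is not, use Weeks 4 and 12 only.
- Show full-follow-up data separately, by cohort, as events per patient-year.
- State how placebo patients are grouped in the safety tables.
- Count AEs from the ADA-extension visits only in the full-follow-up table.

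The cost is SAP wording and a few extra tables. No new data are needed. Late events, including those during Part C dosing after Week 24, appear only in the full-follow-up table. Its rates remain hard to compare between regimens if risk changes over time, so comparisons should rest on the Week 24 table.
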